OCD is an extremely heterogeneous disorder (Radomsky & Taylor, 2005), with multiple presentations of different combinations of symptoms (Pinto, Mancebo, Eisen, Pagano, & Rasmussen, 2006). Perhaps **interventions need to be more targeted to the specific symptoms** and maladaptive beliefs that are at the root of the symptoms. **One of the most commonly reported lifetime symptoms is compulsive checking** (Ruscio, Stein, Chiu, & Kessler, 2010). Rachman's (2002) theoretical account of compulsive checking contains many elements, but among them is the self-perpetuating cycle between doubting and checking. In this cycle, **checking is caused by doubt, but the act of checking paradoxically increases, rather than decreases doubt**, thereby maintaining the urge to check. There is now a robust experimental literature demonstrating that repeated checking, both physical or mental of both virtual or real home appliances, leads to lower confidence in memory of the checks (e.g., Boschen & Vuksanovic, 2007; Coles, Radomsky, & Horng, 2006; Radomsky & Alcolado, 2010; Radomsky, Dugas, Alcolado, & Lavoie, 2014; van den Hout & Kindt, 2003). Other more recent experimental research has demonstrated that the inverse also occurs. Inducing low memory confidence with an experimental paradigm (using false feedback following a memory test) can cause urges to check (Alcolado & Radomsky, 2011). Indeed, if this is true, the **doubt in the OCD cycle may come in part from beliefs one has a poor memory** (see Radomsky & Alcolado, 2010). In line with this hypothesis, research has shown poor memory confidence predicts checking (Nedeljkovic & Kyrios, 2007), and beliefs about poor memory interact with other dysfunctional beliefs related to OCD to predict checking (Cuttler, Alcolado, & Taylor, 2013). There is also evidence to suggest that poor beliefs about memory are related to greater severity of compulsive checking in clinical samples (Nedeljkovic & Kyrios, 2007; Nedeljkovic, Moulding, Kyrios, & Doron, 2009; Alcolado & Radomsky, 2016).

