- 4. Determine for whom the intervention is effective:** This novel CBT intervention for checking (CBT-C) focuses on identifying and challenging maladaptive beliefs about memory, with the aim to increase patients' confidence in their memory for checking situations. In the preliminary treatment investigation, maladaptive beliefs about memory decreased significantly across treatment, and were predictive of decreased checking behaviours at post-treatment (Alcolado & Radomsky, 2016). However, it remains unclear for whom this intervention is most effective. Are all individuals with compulsive checking plagued by maladaptive beliefs about memory, and do patients need to endorse these beliefs in order for this treatment to be effective? These questions will also be examined in this investigation, where the larger sample size will allow for comparisons based on patients' degree of endorsement of maladaptive beliefs about memory.

Hypotheses:

Following directly from the project's objectives, the hypotheses are **(1)** that the treatment (CBT-C) will be effective, in replication of a previous pilot treatment; **(2)** this brief intervention will be more effective than the comparison condition (TAU); **(3)** the effects will be maintained at 6-month follow-

up; and that (4) although the treatment will be effective for all, it will be most effective for those patients with high pre-treatment levels of maladaptive beliefs about memory.

Design/Methodology

Participants:

Participants (N = 50): n = 25 in CBT-C, and n = 25 in TAU; allowing for the testing of an additional 5 participants [predicting an approximate 10% drop-out rate as was seen in the pilot study]) will take part. This sample size is reasonable given the number of OCD referrals our clinic typically receives in a year (approximately N = 50) in conjunction with the active recruitment we will do through the community support groups, allowing for ineligible participants and study attrition. This sample size is also adequately powered for the analyses (see Power Analyses and Statistical Plan, below). Participants will come from one of two sources, either our Anxiety Disorders Clinic or community (see Recruitment, below).

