Inclusion criteria are that participants must be age 18 or older, with a diagnosis of OCD and clinically significant levels of compulsive checking. This is defined as being able to meet the diagnostic criteria for OCD according to the Diagnostic and Statistical Manual of Mental Disorders, 5th Edition (DSM-5; American Psychiatric Association, 2013) based solely on checking symptoms. Other OCD symptoms may be present and checking does not need to be the primary symptom. This study will be offered through online video conferencing platforms or in-person appointments to adhere to pandemic restrictions and maximum safety. If pandemic restrictions are in place, participants must be available for appointments using an online video conference platform such as Zoom, Microsoft Teams, or Doxy.

Exclusion criteria include active suicidality, psychosis, mania, or a substance use disorder that would interfere with participation in the treatment. Participants do not have to be treatment or CBT naïve, and can be medicated, as we are interested in a real-world sample. This information will be collected and tracked in case any differences become relevant for analyses.

Power analyses conducted using G*power (Faul, Erdfelder, Lang, & Buchner, 2007) indicate the sample size of 50 participants will provide more than adequate power to conduct all analyses (see Statistical Plan, below). For the ANOVAs, assuming a medium effect size, 2 conditions, 3 time points, and requiring a high level of power, an N of 44 is needed. For a linear regression with one predictor, with similar effect size and power, N = 43 is needed.

Materials:

Measures: These will include a **background information** form (including age, sex, level of education, marital status, and work status). **The MINI International Neuropsychiatric Interview** (Sheehan et al., 1998) Version 6.0 will be administered to diagnose presence of OCD and any other co-morbid conditions according to the. OCD severity will be assessed using the gold standard **Yale-Brown Obsessive Compulsive Scale** (Y-BOCS; Goodman et al., 1989a). **Validated self-report questionnaires assessing OCD symptoms** (the Vancouver Obsessional Compulsive Inventory [VOCI]; Thordarson et al., 2005), **beliefs** (Obsessive Beliefs Questionnaire [OBQ]; OCCWG, 2005), and associated **affective symptoms** (Depression Anxiety Stress Scale, DASS; Lovibond & Lovibond, 1995) will be administered. To assess beliefs about memory, the new **Beliefs about**

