Compensation: Participants will be offered \$10 at the end of each assessment visit (for a maximum of \$30 per participant), as a monetary compensation for participants time and efforts, as well as to offset the costs of transportation for their appointments. They will not be offered compensation for their treatment visits. Compensation will be offered in-person, or, if a participant attends online visits, will be provided by mail.

Timeline:

Time point	Phone Screen	Pre-treatment Assessment	Treatment Week 1	Treatment Week 2	Post-treatment Assessment	6-mo. follow-up & debrief
Condition						
A) CBT-C	✓	✓	✓	✓	✓	✓
B) TAU	✓	✓	×	×	✓	✓

✓ = Study visit at this time point

× = No study visit at this time point

Statistical Plan:

Intent-to-treat (ITT) analyses will be conducted in order to accurately depict the progression of all participants through this treatment. As such, if there is drop-out, the last observation point for those participants will be carried forward for all subsequent missing data points of interest. To test **hypotheses 1, 2, and 3** (1 - that the treatment be effective, 2 – as compared to the control group, and 3 – that its effects last over the follow-up period), a mixed-model ANOVA will be conducted. The between-participants independent variable will be treatment condition (CBT-C vs. TAU), and the within-participants independent variable will be time point (pre-treatment, post-treatment, and 6-month follow-up). The dependent variable will be the checking subscale of the VOCI. A similar analysis using average daily time spent checking per week from the daily diaries as a dependent variable, as an alternate measure of checking.

A linear regression will be conducted to test **hypothesis 4** (that the extent to which maladaptive beliefs about memory are endorsed affect outcome). Pre-treatment BAMI total score will be entered as the predictor variable. The criterion variable will be a change score that subtracts pre-treatment VOCI score from post-treatment VOCI score. All analyses will be conducted using SPSS statistical software.

Budget details and available resources:

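### The hypothesis 4 regression has no arm-by-BAMI term, so it cannot show that the benefit of CBT-C over TAU depends on memory beliefs, and it may mislead at a rate the documents do not determine

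*Combined protocol and SAP*

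**What the plan says.** The Hypotheses section predicts that CBT-C will help all patients but that "it will be most effective for those patients with high pre-treatment levels of maladaptive beliefs about memory". Study Objective 4 asks the matching question: for whom the intervention works, and whether patients must hold these beliefs to benefit. The background section closes on whether CBT-C beats usual treatment for particular individuals.

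The Statistical Plan restates hypothesis 4 more weakly, as "that the extent to which maladaptive beliefs about memory are endorsed affect outcome", and assigns it a linear regression. On the predictor: "Pre-treatment BAMI total score will be entered as the predictor variable". On the outcome: "The criterion variable will be a change score that subtracts pre-treatment VOCI score from post-treatment VOCI score". The power paragraph under Participants confirms the size of the model: "For a linear regression with one predictor, with similar effect size and power, N = 43 is needed".

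Arm, arm by BAMI, and baseline VOCI do not appear in this model. The plan does not say whether it is fitted in both arms or in CBT-C only. Objective 4 mentions comparisons by degree of belief endorsement, but the Statistical Plan specifies none.

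**The concern.** The hypothesis is about how a treatment difference varies with a baseline characteristic. The test is about whether that characteristic goes with change in general. Patients with strong memory beliefs might improve more in both arms alike, and the planned slope would then look the same as if CBT-C worked better for them.

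The choice of outcome adds a conditional risk. The background section reports that "poor beliefs about memory are related to greater severity of compulsive checking in clinical samples", so high-BAMI patients may start with higher VOCI checking scores. An unadjusted change score can then carry regression to the mean into the BAMI slope, in the direction hypothesis 4 predicts.

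At stake is the answer to Objective 4, namely which patients should be offered CBT-C. This regression is the only analysis assigned to it.

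**Working it through.** **1. The plan's own figure.** N = 43 is reproduced with these assumed settings: f² = 0.15 (a conventional medium effect), alpha 0.05 one-sided, one predictor. The noncentrality is √(0.15 × 43) = 2.54 on 41 df, giving power 80.3%; N = 42 gives 79.5%. A two-sided test at 80% needs 55. Two things follow. First, 43 exceeds the 25 patients per arm, so a pooled fit over both arms is implied. Second, the calculation concerns the overall BAMI slope and says nothing about an interaction.

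**2. What the slope estimates.** Let b be the slope of VOCI change on BAMI in TAU, and b + δ the slope in CBT-C. Hypothesis 4 is a statement about δ, with δ negative because negative change is improvement.

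- Pooled over 1:1 arms, the slope is approximately b + δ/2.
- In CBT-C alone (n = 25), it is b + δ.

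Neither separates δ from b. For example, in SD per SD, b = −0.25 with δ = 0 gives a pooled slope of −0.25. So does b = 0 with δ = −0.5, since 0 − 0.5/2 = −0.25. The first case has no moderation and the second has a good deal.

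**3. Can b be negative without moderation?** Take standardised scores, BAMI-baseline VOCI correlation r and pre-post correlation ρ. Neither is in the documents; I assume r = 0.3 to 0.5 and ρ = 0.5 to 0.8.

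- *Structure A:* BAMI is linked to post-treatment VOCI only through the observed baseline score. Then cov(BAMI, change) = ρr − r = −r(1 − ρ). Apart from the arm effect, var(change) = 2(1 − ρ), so the correlation is −r√((1 − ρ)/2).
- *Structure B:* BAMI is linked to stable checking severity, so its covariance with pre and post is the same. Then cov(BAMI, change) = r − r = 0.

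I simulated 20,000 trials per setting with N = 50 in 1:1 allocation, an equal 0.5 SD effect for everyone and no moderation. The two middle columns count results significant at two-sided 5% in the hypothesised direction (nominal 2.5%).

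| r, ρ | Correlation under A | Planned test, A | Planned test, B | Interaction test, two-sided (A and B) |
|---|---|---|---|---|
| 0.3, 0.8 | −0.3 × √0.10 = −0.095 | 9% | 2.5% | about 5% |
| 0.4, 0.6 | −0.4 × √0.20 = −0.179 | 23% | 2.5% | about 5% |
| 0.5, 0.5 | −0.5 × √0.25 = −0.25 | 40% | 2.5% | about 5% |

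The interaction test is the arm-by-BAMI coefficient in a model that also contains baseline VOCI, arm and BAMI. Under structure A with r = 0.4 and ρ = 0.5, the planned regression fitted in CBT-C alone gives 16% against the same nominal 2.5%.

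**4. Power of the interaction test at N = 50, two-sided 5%.**

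- Slope difference 0.5 SD per SD of BAMI: 48% at ρ = 0.5, 53% at 0.6, and 76% to 77% at 0.8.
- Slope difference 0.7: 74%, 81%, and 95% to 96%.

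The last figures vary by about a point between runs.

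**The case against.** Four points can be made for the plan.

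*The Statistical Plan claims only that beliefs affect outcome.* A one-predictor regression does answer that narrower question. But it is not the question in the Hypotheses section or in Objective 4, and nothing else in the document fills the gap.

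*The regression may be meant for CBT-C only.* The plan does not say so, and N = 43 against 25 per arm points the other way. A CBT-C-only fit would still have no control contrast.

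*The false-positive risk may be nil.* This largely stands. A reader might infer that the planned regression will often report moderation falsely, or that a significant slope is to be expected. The documents do not support that. They report that stronger beliefs go with more severe checking, which supports high-BAMI patients starting higher. It does not establish that they would fall further untreated; that requires BAMI to track the transient part of the baseline score. The background treats memory beliefs as part of what drives checking, so a stable link (structure B, with no inflation) is at least as compatible with the text. Even under structure A, most null trials in the settings examined show no such slope.

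*Some omissions are harmless or only apparent.* Leaving out the arm main effect adds noise under randomisation; it does not inflate error. A reader might also infer that the VOCI total was planned as the outcome for hypothesis 4. The preceding paragraph of the Statistical Plan names the checking subscale, and the later phrase may be shorthand, so this needs clarifying and is not an established error.

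**Conclusion.** The test does not match the hypothesis. This rests on the text alone: hypothesis 4 concerns how the CBT-C effect varies with BAMI, and the model has no term that measures such variation. As written it cannot support hypothesis 4, whatever the result, and it should be replaced.

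The risk of false support is real but of undetermined size. It runs from nominal (about 2.5%) under a stable-severity link to about 9% to 40% if BAMI acts only through the observed baseline score. Both figures assume N = 50, an equal 0.5 SD effect, r = 0.3 to 0.5 and ρ = 0.5 to 0.8. The case for change rests on the missing interaction, not on these rates.

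The randomised comparison for hypotheses 1 to 3 is unaffected. The statement that the calculations "indicate the sample size of 50 participants will provide more than adequate power to conduct all analyses" should not be applied to hypothesis 4, because the only regression calculation is for a different test.

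**What to change.** Replace the regression with one linear model fitted in both arms:

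post-treatment VOCI checking subscale = baseline VOCI checking subscale + arm + centred baseline BAMI + arm × BAMI.

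- Base hypothesis 4 only on the arm × BAMI coefficient, and state the alpha and sidedness.
- Report the adjusted CBT-C minus TAU difference, with 95% confidence intervals, at mean BAMI and at one SD above and below it.
- State that the VOCI score for hypothesis 4 is the checking subscale used for hypotheses 1 to 3.
- Align the wording of hypothesis 4 in the Statistical Plan with the Hypotheses section.
- Label hypothesis 4 exploratory, and exclude it from the claim of adequate power for all analyses.

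The cost is a few sentences. The data and SPSS stay the same. The budget section counts three completers and 47 participants still to recruit, so the change can still be prespecified. The downside is limited power: about 48% to 76% for a slope difference of 0.5 SD per SD of BAMI, and 74% to 95% for 0.7, over assumed pre-post correlations of 0.5 to 0.8. A non-significant interaction should therefore not be read as showing that CBT-C works equally well at every level of belief.
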